### **Primary and Secondary Efficacy Endpoint**

Primary and secondary objectives will be measured using the next efficacy endpoints:

1. Fat thickness measurements using Ultrasound device

 Syneron Medical Ltd. Confidential	Clinical Study to Evaluate the Safety and Efficacy of the SlimShape Device for Abdominal Fat and Circumference Reduction			
	Protocol #	DHF22621	Rev. Date	October 8, 2017

2. Fat thickness measurements using Calibrated Caliper device
3. Circumference measurements of the abdominal area using Measuring Tape
4. Investigator satisfaction using a pre-defined scale
5. Subject improvement and satisfaction using a pre-defined scale
6. Photography

### **Primary Safety Endpoint**

The number, severity and type of any adverse event recorded throughout the study and post treatment (discomfort (pain), immediate and delayed response).

1. Occurrence of expected post treatment immediate response including erythema and edema and during all study period based on predefined scale (Table 4).
2. Number, severity and type of any adverse event recorded throughout the course of the study.

## **STUDY POPULATION**

### **Number of Subjects**

This study will be comprised of up to 120 subjects in up to ten (10) investigational sites. Subjects who meet all the inclusion and none of the exclusion criteria will be enroll.

### **Subject Withdrawal and Replacement**

Subjects enrolled in the study can discontinue their participation at any time for any reason without prejudice or reduction in the quality of their medical care. The investigators or sponsor can terminate a subject's participation in this study to protect the subject's health or if the subject fails to follow directions resulting in noncompliance to study procedures. Subjects who withdraw or are terminated from the study may be replaced to ensure at least 120 subjects have completed the study. Subjects who fail to complete the treatment will be replaced and will not be evaluable.

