**TABLE 1- STUDY SYNOPSIS**

Proprietary Name	SlimShape device
Design	
Prospective, one arm, baseline-controlled, clinical study for the evaluation of the SlimShape device for non-invasive abdominal fat and circumference reduction.
 
Study subjects will undergo SlimShape treatments on the abdominal area

Study Population	Up to 120 healthy adult volunteers, seeking for noninvasive abdominal fat and circumference reduction, male and females, 18 to 60 years of age from up to 10 investigational sites.
Treatment and Duration	
Eligible subjects will receive up to 3 bi-weekly treatments (2 weeks interval) with the SlimShape device utilizing the SlimShape Applicator Belt according to the study protocol.
 
The subject will return for 3 follow up visits: four weeks (4wk FU), eight weeks (8wk FU) and 12 weeks (12wk FU) after the last treatment.
 
Each subject will be enrolled for total expected study duration of up to 16 weeks.

Objective	The objective of this trial is to evaluate the safety and efficacy of the SlimShape device utilizing the SlimShape Applicator Belt for abdominal non-invasive fat and circumference reduction
Primary Objective	Statistically significant abdominal fat reduction post SlimShape treatments at 12 weeks follow-up (12wk FU) versus baseline
Primary Safety Objective	Evaluate the safety of the treatment with the SlimShape device utilizing the SlimShape Applicator Belt during all study
Secondary Objectives	
 
1. Statistically significant abdominal fat reduction post SlimShape treatments as measured by Ultrasound device at Pre Tx.3, 4 weeks, and 8 weeks follow-up (4wk FU and 8wk FU) versus baseline
 
2. Statistically significant abdominal fat reduction post SlimShape treatments as measured by calibrated Caliper device at Pre Tx.3, 4 weeks, 8 weeks and 12 weeks follow-up (4wk FU, 8wk FU and 12wk FU) versus baseline
 
3. Statistically significant abdominal circumference reduction post SlimShape treatment/s at Pre Tx.2, Pre Tx.3, 4 weeks, 8 weeks and 12 weeks follow-up (4wk FU, 8wk FU and 12wk FU) versus baseline
 
4. Investigator satisfaction: 
Satisfaction assessment will be performed by the study investigator using a pre-defined scale questionnaire. The investigator will answer this questionnaire at each follow-up visit (4wk FU, 8wk FU and 12wk FU)
 
 

Protocol #

DHF22621

Rev. Date

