**STUDY DESIGN OVERVIEW**

This study is a prospective, baseline controlled, multi-center, one arm clinical study showing the performance and safety of the SlimShape treatment for abdominal non-invasive fat and circumference reduction.

Up to 120 Healthy subjects in up to 10 investigational sites will be enrolled in this study. All subjects will undergo an assessment of their general health. During the treatment period, subject's fat thickness and circumference will be measured and up to three successive bi-weekly (two weeks interval) treatments will be performed.

The study subjects will undergo treatments with SlimShape device utilizing the SlimShape Applicator Belt.

During the follow-up period visit will be conducted as follow: 4 weeks (4wk FU), 8 weeks (8wk FU) and 12 weeks (12wk FU) post last treatment. Subject's fat thickness will be measured using 2 different methods (Calibrated Caliper and Ultrasound Imaging (USI)) and fat reduction will be assessed at each post baseline visit. Circumference will be measured in 3 measurements heights and circumference reduction will be assessed at each post baseline visit. Additionally, investigator and subject questionnaires will be completed. Finally, photography will be performed under visible light conditions of the front, right, left and back view. Most of the assessments will occur at each of the visits to the clinic.

 Syneron Medical Ltd. Confidential	Clinical Study to Evaluate the Safety and Efficacy of the SlimShape Device for Abdominal Fat and Circumference Reduction			
	Protocol #	DHF22621	Rev. Date	October 8, 2017

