## **Return Visits**

All subjects will be requested to return to the clinic at the following time-points during the study in order to assess the clinical performance of the device:

- Visit 4: FU1 – 4 weeks ( $\pm 7$  days) post last treatment.
- Visit 5: FU2 – 8 weeks ( $\pm 7$  days) post last treatment.
- Visit 6: FU3 – 12 weeks ( $\pm 7$  days) post last treatment.

At each return visit the following procedures will be conducted and data recorded:

- Weight.
- Ultrasound fat-thickness measurements.
- Caliper fat-thickness measurements.
- Circumference measurements.
- Skin assessment for clinical effects due the procedures:
  - Post treatment response and adverse events.
- Photographs as conducted at baseline.
- Satisfaction questionnaire performed by the investigator using the Global Aesthetic Improvement (GAI).
- Completion of the Subject Follow Up questionnaire:
  - Subjective Improvement and satisfaction performed by the subject using the Global Aesthetic Improvement (GAI).
- At the final visit a urine pregnancy test will be performed for women with childbearing potential.

 Syneron Medical Ltd. Confidential	Clinical Study to Evaluate the Safety and Efficacy of the SlimShape Device for Abdominal Fat and Circumference Reduction			
	Protocol #	DHF22621	Rev. Date	October 8, 2017

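### Subjects who do not complete treatment are declared not evaluable, which would exclude the 12-week ultrasound of any who still attend; separately, 120 is both the most enrolled and the fewest completed

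*Combined protocol and SAP*

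**What the plan says.** Subject Withdrawal and Replacement contains two rules. Subjects who withdraw or are terminated "may be replaced to ensure at least 120 subjects have completed the study". The next sentence reads: "Subjects who fail to complete the treatment will be replaced and will not be evaluable". Replacement is optional in the first rule and mandatory in the second, and only the second says anything about evaluability.

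No section defines an analysis set or a method for missing data. The Recording section under Data Analysis foresees analysis of all collected data as the protocol describes, but names no population.

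Return Visits states: "All subjects will be requested to return to the clinic at the following time-points during the study". The visits fall 4, 8 and 12 weeks after the last treatment, and the procedures at each include "Ultrasound fat-thickness measurements". The Primary Objective is a statistically significant reduction in ultrasound fat thickness from baseline to the 12-week visit. Treatment Procedure allows up to three treatments, the number being left to the investigator.

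On numbers, Study Design Overview says "Up to 120 Healthy subjects in up to 10 investigational sites will be enrolled in this study", Number of Subjects says "This study will be comprised of up to 120 subjects in up to ten (10) investigational sites", and the synopsis says "Up to 120 healthy adult volunteers, seeking for noninvasive abdominal fat and circumference reduction".

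**The concern.** The study has one arm and is its own control. If subjects are removed after treatment has begun, any difference in response between them and the completers passes directly into the estimated mean change, with no comparator to absorb it. Refilling the sample restores the count but not the mix of subjects. If a removed subject has a 12-week ultrasound, the loss is avoidable, because the visit that supplies it is already in the schedule.

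The exclusion also has no fixed boundary. With the number of sessions left to the investigator, the same one- or two-session course could be classed as complete or as a failure to complete.

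Separately, the three statements that cap the study at 120 subjects clash with a replacement rule that aims for at least 120 completers. The reader cannot tell whether 120 is an enrolment number or a completer target.

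**Working it through.** **The plan's own figure.** 120 cannot be reproduced. The documents give a two-sided alpha of 0.05 but no effect size, standard deviation, power or loss rate. All rates below are therefore assumptions.

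**Step 1: who could be excluded despite having data.** The follow-up visits are timed from the last treatment. At the nominal 2-week interval, the 12-week visit falls at 2 × (sessions − 1) + 12 weeks after the first treatment: week 12, 14 or 16 for one, two or three sessions. All three fit the synopsis statement "Each subject will be enrolled for total expected study duration of up to 16 weeks". A subject who stops early but keeps attending would thus have three follow-up ultrasounds, including the primary one, and could still be not evaluable. A subject who leaves the study has no 12-week value to exclude.

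**Step 2: effect on the mean.** Let d be the proportion not completing treatment and r their mean change divided by that of completers. The completers' mean differs from the all-treated mean by 1/((1 − d) + d·r) − 1. For d = 0.10 and r = 0 this is 1/0.90 − 1 = 11.1%.

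| d | r = 0 | r = 0.5 | r = 1 | r = 1.5 |
|---|---|---|---|---|
| 5% | +5.3% | +2.6% | 0 | −2.4% |
| 10% | +11.1% | +5.3% | 0 | −4.8% |
| 20% | +25.0% | +11.1% | 0 | −9.1% |

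If the clause is deleted and a fraction f of non-completers is measured at 12 weeks, the r = 0 overstatement becomes 1/((1 − d) + f·d) − 1. At f = 0.5 it is 2.6%, 5.3% or 11.1% for the three values of d; at f = 1 it is 0.

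**Step 3: effect on the test.** The Statistical Methods row names the paired t-test and/or Wilcoxon signed rank test for circumference and questionnaire data; I assume a paired t-test for ultrasound too. Let m be the completers' mean change in standard deviation units (assumed). Adding the non-completers as exactly unchanged multiplies t by 1/√(1 + d·m²):

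| m | d = 5% | d = 10% | d = 20% |
|---|---|---|---|
| 0.3 | 0.998 | 0.996 | 0.991 |
| 0.5 | 0.994 | 0.988 | 0.976 |

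Example: 120 completers with m = 0.3 give t = 0.3 × √120 = 3.29. Adding 30 unchanged subjects (d = 30/150 = 0.20) gives 3.29 × 0.991 = 3.26. The mean falls by a fifth and the test hardly moves.

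**Step 4: the 120.** Let L be an assumed loss from the study. Enrolment needed for 120 completers is 120/(1 − L), rounded up. Completers under the cap are 120 × (1 − L). The confidence interval widens by 1/√(1 − L) relative to 120 completers.

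| L | Enrolment needed | Completers under the cap | Interval width ratio |
|---|---|---|---|
| 5% | 127 | 114 | 1.026 |
| 10% | 134 | 108 | 1.054 |
| 20% | 150 | 96 | 1.118 |

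The two limits agree only with exactly 120 enrolled and no loss. At L = 5% with independent losses, the chance of no loss is 0.95^120 = 0.002.

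**The case against.** The strongest reply is that the disputed sentence stands under a heading on withdrawal, directly after a sentence about subjects who withdraw or are terminated. Read that way, it covers people who have left and would normally have no 12-week ultrasound. The follow-up visits are also numbered 4, 5 and 6, which presupposes three treatment visits; follow-up after an early stop is not described. This stands in part. A reader might infer that the plan certainly discards 12-week data, but the documents do not say whether stopping treatment ends participation, so the exclusion applies only if such subjects still attend. The request to all subjects carries no exception, however, and the sentence itself refers to failing to complete treatment, not to leaving the study.

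Second, if completing treatment means the course the investigator chose, a subject given one or two sessions is evaluable. That stands: a reader should not infer that everyone with fewer than three sessions is excluded. Nor do the documents say that evaluability would be decided after results are seen; the undefined term merely leaves this open.

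Third, the primary objective is significance, and Step 3 shows that unchanged non-completers barely affect it. That stands as well, and limits the consequence mainly to the estimated mean.

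Finally, a reader might infer that these subjects also drop out of the safety count. The Primary Safety Endpoint and Safety sections cover events throughout the study, so that is not claimed here.

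**Conclusion.** The point holds in conditional form and should be fixed. The plan states an exclusion based on what happens after treatment starts, gives no other analysis set, and leaves the criterion undefined. Where a subject stops treatment but attends at 12 weeks, an observed primary measurement would be left out.

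The size and sign of any bias are unknown. The range from +25% to −9% in Step 2 rests wholly on assumed non-completion of 5% to 20% and assumed relative response; bias is zero if non-completers respond like completers. A reader might infer that the device's effect would be overstated or that a significant result would be unsafe. The documents support neither.

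The conflict over 120 is certain as a matter of arithmetic, but its effect on precision is modest: intervals 2.6% to 11.8% wider at an assumed 5% to 20% loss if the cap holds.

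**What to change.** 1. In Subject Withdrawal and Replacement, delete the part of the sentence that makes treatment non-completers not evaluable.
2. Define the primary efficacy set as all subjects with at least one treatment and a baseline ultrasound. Use every observed 12-week ultrasound, whatever the number of treatments received. Keep a completers analysis as supportive.
3. State the primary method for missing 12-week values: for example, a mixed model over the ultrasound visits, or the paired test on observed 12-week values with the number missing reported. A mixed model adds no information on response for subjects without any post-baseline ultrasound. Add a sensitivity analysis that sets missing values to no change from baseline, and a tipping point: the mean increase in these subjects at which significance is lost. The tipping point is needed because Step 3 shows that the no-change fill scarcely tests the conclusion.
4. Reconcile Subject Withdrawal and Replacement, Treatment Procedure and Return Visits on what completing treatment means and whether subjects who stop early remain in follow-up, consistently with the existing termination provision. The number of treatments and any discontinuation rule are for the sponsor.
5. State 120 once, as either the enrolment number or the completer target, and align the synopsis, Study Design Overview, Number of Subjects and Subject Withdrawal and Replacement.

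The cost is wording and the added sensitivity analysis. No new visits are needed if Return Visits is confirmed to apply to subjects who stop early. The mean change may come out somewhat smaller, some subjects will have partial data, and the enrolment cap must be restated if 120 is the completer target.

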### **Inclusion Criteria**

A subject is eligible to participate in the study if he/she meets all the following inclusion criteria:

1. Signed informed consent to participate in the study.
2. Female and male subjects,  $\geq 18$  and  $\leq 60$  years of age at the time of enrolment
3. Fitzpatrick Skin Type I to VI
4. BMI interval:  $18.5 \leq \text{BMI} \leq 30$  (normal to overweight, but not obese).
5. If female, not pregnant, lactating and must be either post-menopausal, surgically sterilized, or using a medically acceptable form of birth control at least 3 months prior to

 Syneron Medical Ltd. Confidential	Clinical Study to Evaluate the Safety and Efficacy of the SlimShape Device for Abdominal Fat and Circumference Reduction			
	Protocol #	DHF22621	Rev. Date	October 8, 2017

- enrollment (i.e., oral contraceptives, contraceptive implant, barrier methods with spermicide or abstinence).
6. In addition, negative urine pregnancy test as tested before each treatment and at the last visit for women with childbearing potential (e.g. not menopause).
  7. General good health confirmed by medical history and skin examination of the treated area.
  8. Willing to follow the treatment and follow-up schedule and post-treatment care instructions.
  9. Willing to refrain from a change in diet/ exercise/medication regimen for the entire course of the study.
  10. Willing to have photographs and images taken of the treated areas to be used de-identified in evaluations, publications and presentations.

### **Exclusion Criteria**

A subject is not eligible for participation in this study if he/she meets any of the following exclusion criteria:

1. History of hypertension, ischemic heart disease, valvular heart disease, congestive heart failure, pacemaker/defibrillator, abdominal aortic aneurism
2. Current hyperlipidemia, diabetes mellitus, hepatitis, liver disease, HIV positive status, blood coagulopathy or excessive bleeding, autoimmune or connective tissue disease
3. Having or undergoing any form of treatment for active cancer, or having a history of skin cancer or any other cancer in the areas to be treated, including presence of malignant or pre-malignant pigmented lesions
4. Having any active electrical implant anywhere in the body, such as a pacemaker or an internal defibrillator
5. Having a permanent implant in the treated area, such as metal plates or an injected chemical substance such as silicone
6. Having undergone any other surgery in the treated areas within 12 months of treatment or during the study, including liposuction
7. Previous body contouring procedures in the treatment area within 12 months
8. History of skin disease in the treatment area, known tendency to form keloids or poor wound healing
9. History of epidermal or dermal disorders (particularly if involving collagen or microvasculature)
10. Suffering from significant skin conditions in the treated areas or inflammatory skin conditions, including, but not limited to, open lacerations or abrasions and active cold

 Syneron Medical Ltd. Confidential	Clinical Study to Evaluate the Safety and Efficacy of the SlimShape Device for Abdominal Fat and Circumference Reduction			
	Protocol #	DHF22621	Rev. Date	October 8, 2017

- sores or herpes sores prior to treatment (duration of resolution as per the Investigator's discretion) or during the treatment course
11. Allergy to any component of the lotion (VelaSpray Ease) used in this study
  12. Skin lesions in the treatment area other than simple nevi on physical examination (e.g., atypical nevus, tattoo, abrasions) including depressed scars in the treatment area
  13. Very poor skin quality (i.e., severe laxity)
  14. Abdominal wall diastasis or hernia on physical examination
  15. Abnormal kidney, liver or coagulation functions, abnormal lipid profile or blood count within the last 3 months
  16. Obesity (BMI > 30)
  17. Childbirth within the last 12 months or breastfeeding women. Any acute or chronic condition which, in the opinion of the investigator, could interfere with the conduct of the study
  18. Unstable weight within the last 6 months (i.e.,  $\pm$  3% weight change in the prior six months)
  19. Inability to comply with circumference measurement procedure (e.g., inability to hold breath for the required duration).
  20. Participation in another clinical study involving same anatomical areas within the last 6 months (or 30 days in case different anatomical areas were treated in previous trial/s).
  21. As per the Investigator's discretion, any physical or mental condition which might make it unsafe for the subject to participate in this study.

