## 5. Subject improvement and satisfaction:

Improvement and satisfaction assessment will be performed independently by the subject using a pre-defined scale questionnaire. The subjects will answer this questionnaire at each follow-up visit (4wk FU, 8wk FU and 12wk FU)

 Syneron Medical Ltd. Confidential	Clinical Study to Evaluate the Safety and Efficacy of the SlimShape Device for Abdominal Fat and Circumference Reduction			
	Protocol #	DHF22621	Rev. Date	October 8, 2017

Efficacy Endpoints	Primary and secondary objectives will be measured using the next efficacy endpoints: 
 
1. Fat thickness measurements using Ultrasound device
 
2. Fat thickness measurements using Caliper
 
3. Circumference measurements of the abdominal area using Measuring Tape
 
4. Investigator satisfaction using a pre-defined scale
 
5. Subject improvement and satisfaction using a pre-defined scale
 
6. Photography
 

Safety Endpoints	
 
1. The number, severity and type of any adverse event recorded throughout the study and post treatment (immediate and delayed response)
 

Statistical Methods	Descriptive statistics will be used to present changes in the assessments along the study course. Circumference measurements and subject assessments' and satisfaction data will be analyzed using two-tailed Wilcoxon Signed Rank test and/or paired t-test (alpha=0.05) to analyze the data difference from baseline and longitudinal change.

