### **Primary Objective**

Statistically significant abdominal fat reduction as measured by Ultrasound Imaging device post SlimShape treatments at 12 weeks follow-up (12wk FU) versus baseline.

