### **Screening**

1. ICF - Prior to any study procedures, informed consent will be obtained. When the subject fully understands the possible benefits and risks of the study, the subject will be asked to sign and date the informed consent form (ICF). The subject will be given a copy of the signed ICF.
2. Subject ID - subjects will be assigned a study subject ID number.
3. Medical History - A medical history will be obtained to determine if the subject meets the study criteria, including a list of all prescribed and over the counter medications taken within the previous 6 months will be recorded.
4. Skin Exam - The subject will undergo a routine skin exam to determine if they meet the study criteria including the presence of fatty tissue deposits in the treatment area.
5. BMI – the volunteers’ height and weight will be taken for calculation of BMI.
6. Pregnancy Screen - Subjects who are capable of becoming pregnant will undergo a urine pregnancy test. This will be repeated prior to all treatments, and at the end of the study (last FU visit/ 12wk FU). If the Screening and Treatment procedures are not conducted on the same day, the urine pregnancy test will be repeated on the first treatment day.
7. Scheduling: Subjects will be scheduled to return for the baseline and first treatments visit within 14 days following the screening visit. It is preferable the baseline procedures and Tx.1 will be conducted immediately after the Screening visit.

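### Eligibility admits slow or recently started weight loss, and no planned analysis of fat thickness or circumference takes weight change into account

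*Combined protocol and SAP*

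**What the plan says.** **Weight history.** Exclusion Criteria, item 18, excludes "Unstable weight within the last 6 months" and defines it as "3% weight change in the prior six months", in either direction. The limit looks backward only.

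**Regimen during the study.** Inclusion Criteria, item 9, requires subjects to be "Willing to refrain from a change in diet/ exercise/medication regimen for the entire course of the study". It restricts change and is silent on what the regimen may be.

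**Screening.** Item 3 of the Screening section records "a list of all prescribed and over the counter medications taken within the previous 6 months". No criterion refers to weight-loss drugs on that list. Diet and exercise at entry are recorded in neither Table 2 nor the Appendix I schedule.

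**Population and design.** Table 1 describes volunteers "seeking for noninvasive abdominal fat and circumference reduction" and a "Prospective, one arm, baseline-controlled, clinical study".

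**Primary objective.** "Statistically significant abdominal fat reduction as measured by Ultrasound Imaging device post SlimShape treatments at 12 weeks follow-up (12wk FU) versus baseline".

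**Analysis.** Statistical Methods in Table 1 names a "two-tailed Wilcoxon Signed Rank test and/or paired t-test (alpha=0.05", two-sided) for circumference and for subject assessment and satisfaction data. It names no test for ultrasound thickness and no covariate.

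**Weight on study.** Table 2 schedules weight before each treatment and at each follow-up. Follow-up Visit Measurements, under Data Analysis, compares it with baseline.

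**The concern.** A frozen regimen keeps fat thickness constant only if the subject was in energy balance when it was frozen. If the regimen was already producing weight loss, keeping to it faithfully prolongs the loss. The bias therefore arises under perfect compliance with inclusion 9, and better adherence monitoring would not remove it.

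Continuing weight loss would tend to lower the ultrasound, caliper and tape readings together, always in the direction of success. With baseline as the only comparator, nothing subtracts it. At stake is whether a significant fall at 12 weeks can be attributed to the device.

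**Working it through.** **1. Who can enter.** I read all 10 inclusion and 21 exclusion criteria for anything that would stop a subject who is currently slimming.

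- Inclusion 9 bars a change of regimen, so a continuing weight-loss regimen satisfies it.
- Exclusion 18 removes anyone whose weight has already moved 3% in six months.
- The discretionary clauses in exclusions 17 and 21 concern a condition, not a regimen.
- No other item mentions diet, exercise or weight-loss products.

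Two groups remain eligible: slow losers under 3% in six months, and recent starters who have not yet reached 3%. Pre-Treatment Procedures expects screening, baseline and first treatment at one visit, so there will usually be no second pre-treatment weight to reveal a loss in progress.

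**2. Length of exposure.** Two 2-week treatment intervals plus 12 weeks of follow-up: 2 + 2 + 12 = 16 weeks. This agrees with the duration in Table 1.

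**3. Slow loser.** Take six months as 26 weeks and a constant rate just under the limit: 3% × 16/26 = 1.85% of body weight over the study.

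**4. Recent starter.** The rates are assumed. Weeks on the regimen before exclusion 18 applies = 3% / rate. Loss over the study = rate × 16, a linear projection and so an upper bound.

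| Assumed rate per week | Eligible for up to | Projected loss over 16 weeks |
|---|---|---|
| 0.25% | 12 weeks | 4% |
| 0.5% | 6 weeks | 8% |
| 1% | 3 weeks | 16% |

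**5. How small a mean fall is significant.** The protocol gives no power calculation, effect size or SD, so there is no stated figure to reproduce. I assume a two-sided 0.05 paired t-test on ultrasound change with n = 120. The smallest significant mean fall is t(0.975, 119)/√120 = 1.980/10.954 = 0.18 SD of the within-subject change.

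**6. Chance of a significant reduction with no device effect.** Let a share p of subjects have a regimen-driven fall of d, in units of the SD of change among the others. Approximately,

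chance = Φ( p·d·√120 / √(1 + p(1 − p)d²) − 1.96 ).

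For p = 0.10 and d = 1: 1.095/1.044 − 1.96 = −0.91, giving 0.18. Simulation of 20,000 trials per cell gave:

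| Share p | d = 0.5 SD | d = 1 SD |
|---|---|---|
| 0% | 2.6% | 2.4% |
| 5% | 4.2% | 7.8% |
| 10% | 7.6% | 17.6% |
| 20% | 18.5% | 52.1% |

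The 0% row is the nominal 2.5% within simulation error. Both p and d are assumptions, as the documents give neither.

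**The case against.** The strongest reply is that exclusion 18 and inclusion 9 belong together: enrol people whose weight is stable, then hold their habits constant. That is a sensible safeguard, and it works for anyone who has already lost 3%. A reader might infer that any subject already slimming qualifies. The documents do not support that, because the 3% definition in item 18 removes those subjects.

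Four further points carry weight.

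- The slow-loser route is modest, at about 1.85% of body weight.
- A recent starter is eligible only during a limited window, and nothing in the protocol suggests what share of enrolled subjects would be in it. Table 1 says that volunteers want fat reduction. It does not say that they are dieting.
- The SD shifts in the table are not tied to any millimetre or kilogram value, and the milder assumptions give only 4 to 8%.
- Weight is measured at every visit, so a large loss would be visible. It would be wrong to say that the plan is blind to it.

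What remains is that visibility is not control. The protocol compares weight with baseline, but it sets no on-study limit, defines no weight-stable analysis and makes no adjustment of fat thickness or circumference. Inclusion 9 is also only a statement of willingness, although this point does not depend on subjects breaking it.

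**Conclusion.** The point holds in a limited form. The backward-looking 3% limit and the frozen regimen together admit slow or recently started weight loss, and no planned analysis of fat thickness or circumference uses the weight data to separate that loss from a device effect. The bias runs towards success.

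Its size is uncertain. Under the assumed t-test at n = 120, the chance of a falsely significant reduction runs from about 4% (5% of subjects shifted by 0.5 SD), through 8% (10% at 0.5 SD, or 5% at 1 SD) and 18 to 19% (10% at 1 SD, or 20% at 0.5 SD), to 52% (20% at 1 SD), against a nominal 2.5%. The upper end should not be read as a forecast: the share of such subjects and the SD of change are unknown, and the protocol names no test for ultrasound. A reader might also infer that a positive result would be due to weight loss. The documents do not show that; they show only that the plan could not rule it out. This is a cheap improvement, not a fatal flaw.

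**What to change.** 1. **Eligibility.** Extend exclusion 18 to subjects currently following a weight-reduction diet, taking a weight-loss drug or supplement, or on a recently started exercise programme intended for weight loss. Ask and record this at screening, beside the six-month medication list.

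2. **Subjects already enrolled.** Record their regimen status at entry and repeat the primary analysis without those on such a regimen. This relies on recall, so it should be reported as supportive.

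3. **Analysis.** Using the weights already collected, pre-specify a sensitivity analysis of the primary endpoint. It can be done in weight-stable subjects, for example those within the plan's own 3% of baseline weight, or with weight change as a covariate, reporting the expected ultrasound change at zero weight change. A 3% band would keep the slow loser at 1.85%, so the covariate model is the more informative of the two for that group. Weight change occurs after treatment and could in principle include some device effect, so either analysis should stand beside the primary result and not replace it.

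**Cost.** One exclusion clause, one screening question and one more analysis. A few volunteers are screened out, and recruitment may be slightly slower.
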